6.4 Efficacy Evaluation

All efficacy analyses will be performed using the FAS.

6.4.1 Primary Efficacy Outcome Analysis

The primary efficacy endpoint is the change in office-measured (mean of last 2 of 5 unattended measurements using an automated oscillometric sphygmomanometer device after approximately 5

minutes of rest in the seated position) SBP from baseline to the end of Study Week 8. The AOBP mean measure recorded in the external data (denoted 'average') will be used for analysis.

6.4.1.1 Primary Estimand

The Primary Estimand is designed to answer the research question on the treatment effect of investigational therapy in addition to standard of care (SOC) vs. placebo in addition to SOC on the change in office blood pressure from baseline to Week 8.

This Estimand is constructed in line with ICH E9 (R1) addendum. The five components that define the Estimand of interest are:

- Treatment is 5 MLS-101 dose levels (12.5 mg BID, 25 mg BID, 12.5 mg QD, 50 mg QD, or 100mg QD) vs placebo, regardless of compliance.
- Population: Patients with uncontrolled hypertension (hypertensive despite receiving ≥ 2 antihypertensives) as defined by the inclusion/exclusion criteria in the protocol.
- Patient-level outcome / variable: Change in office-measured SBP from baseline to Week 8.
- Population-level summary: Mean (SD) change in office SBP from baseline to Week 8.
- Inter-current events:

The following Intercurrent Events (ICE) have been identified which could prevent measurement of the primary outcome or change the interpretation of the measured primary outcome:

1. Initiation of rescue medications
2. Death before the completion of 8 weeks period (except #5)
3. Patient withdrawal from treatment before the completion of 8 weeks period for treatment-related reason or worsening (defined as reason for treatment withdrawal being "Adverse Event" or "Physician Decision").
4. Patient withdrawal from treatment before the completion of 8 weeks period for non-treatment related reason
5. Death due to COVID-19 / Accidental death

Event 1 will be treated as treatment failure. The observed SBP that triggered rescue medication will be imputed.

Events 2 and 3 will be handled as treatment failure. The baseline value will be imputed.

Events 4 and 5 will be handled using a hypothetical strategy assuming that the clinical course for either treatment group follows their own group with the estimate of the endpoint value obtained using MMRM in the primary analysis.

6.4.1.2 Primary Efficacy Analysis

The primary efficacy endpoint is the Week 8 change from baseline in SBP. The primary efficacy analysis will be performed using a mixed model repeated measures (MMRM) approach with fixed effects of categorical terms for treatment, week, and treatment by week interaction, and baseline SBP as a fixed continuous covariate. In this model, the subject is considered as a random effect, where an unstructured variance/covariance matrix is assumed for describing the correlation of repeated measurements over time.

In case of non-convergence of the model estimates under the unstructured covariance, alternative covariance structures will be considered in the following order: Toeplitz, AR(1), CS.

A least-square estimate, along with the 90% CI, of the mean difference between each dose group and the placebo group will be provided for Week 8. P-values corresponding to the pairwise tests, not adjusted for multiplicity, of the difference between each dose group vs placebo will also be provided.

6.4.1.3 Primary Efficacy Analysis for Part 2

To evaluate the impact of PRA levels at baseline, change from baseline to Week 4 and Week 8 in office-measured SBP will be analyzed using an ANCOVA model with binary PRA (< 1 ng/mL/h versus ≥ 1 ng/mL/h) as a factor and baseline SBP as a covariate, in the subset of subjects randomized to receive 100 mg QD.

A least-square estimate for the mean difference between the PRA groups, along with the 90% CI and associated p-value, will be provided.

The observed value and change from baseline in office-measured SBP at each visit will be summarized using descriptive statistics for the following three treatment groups:

- Part 1 100 mg QD
- Part 2 100 mg QD
- Pooled Placebo from Parts 1 and 2.

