**Statistical Methods:**

[figure not shown]
The primary estimand in the study aims to answer the research question on the treatment effect of investigational therapy versus placebo in addition to standard of care on the change in office-measured blood pressure from baseline to Week 8. Data summaries for this study will be primarily descriptive in nature. Both safety and efficacy will focus on subjects receiving at least 1 dose of study treatment. Endpoints measured as categorical outcomes (including binary endpoints) will be summarized as frequencies and percentages. Continuous endpoints will be summarized using the following descriptive statistics: sample size, mean, median, quartiles and standard deviation. For efficacy endpoints, confidence intervals and tests of significance will use a 10% (2-sided) significance level. Given the exploratory nature of this study, no adjustments for multiplicity will be used.

*Sample Size*

This study has been designed to provide preliminary information regarding the appropriate dose and frequency of dosing for MLS-101 with respect to changes in SBP after 8 weeks of treatment. The sample size has been determined to provide estimates of the placebo-adjusted mean change in SBP from baseline for each dose that are of adequate precision assuming a 90% 2-sided confidence interval and an effect size of 10.0. With 30 subjects planned per arm in Part 1, the mean placebo adjusted change from baseline in SBP for each dose will be estimated with a precision of  $\pm 3.8$ , assuming a standard deviation of 9 in the subject level changes in SBP from baseline. All analyses based on Part 2 of the study will be exploratory in nature; no formal sample size considerations will be made for Part 2.

The study schema for Study MLS-101-201 is presented in [Figure 1](#). The SoA are presented in [Table 1](#) and Table 2 for Part 1 and Part 2 of the study, respectively. Detailed descriptions of study assessments are provided in [Section 4.8](#) and [Section 8](#).

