All secondary efficacy endpoints analyses will be considered supportive and any inferential statistics will be considered descriptive in nature. No adjustment for multiplicity will be performed. Further details of the estimand definition, analysis model, sensitivity and supplementary analyses, including the analyses of the data collected after Study Week 8, are given in the SAP.

Efficacy analyses will be repeated using the FAS subset of 100 mg treatment groups in order to evaluate whether there are any differences in the treatment effect depending on the levels of PRA at baseline.

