2 STUDY DESIGN

2.1 Introduction

This is a Phase 2 randomized, double-blind, placebo-controlled, dose-ranging, multicenter study designed to evaluate the effect of orally administered MLS-101 on BP for the treatment of uncontrolled hypertension (hypertensive despite receiving ≥ 2 antihypertensives) when used as add-on therapy to stable background treatment in male and female subjects ≥ 18 years of age.

The study consists of two parts. For enrollment into Part 1 of the study, a subject's value of PRA must be ≤ 1 ng/mL/h based on morning measurement. If the value of PRA > 1 ng/mL/h based on morning measurement, then subjects may be eligible to enter Part 2 of the study.

The initial estimate is that approximately 1100 subjects will undergo up to 2 weeks of pre-Screening for Part 1 and 4 weeks of pre-Screening for Part 2. It is estimated that approximately 270 subjects will have qualifying plasma renin activity (PRA) and serum aldosterone levels to be eligible to enter Screening/start of Placebo Run-in for Part 1 after completing a Screening/main study informed consent form (ICF) that has been approved by the Institutional Review Board (IRB). Assuming a 40% screen-failure rate during Run-in, a total of 160 subjects will meet all eligibility requirements to qualify for enrollment in the study.

For Part 2, it is estimated that approximately 60 subjects will have qualifying PRA and serum aldosterone levels to be eligible to enter Screening/start of Placebo Run-in for Part 2 after completing a Screening/main study ICF that has been approved by the IRB. Assuming an approximately 40% screen failure rate, a total of 36 subjects will meet all eligibility requirements to qualify for enrollment in Part 2 of the study.

In the previous version of the protocol, subjects in Part 1 of the study were randomized into 6 equal treatment groups (1:1:1:1:1:1) to 12.5 mg BID, 25 mg BID, 12.5 mg QD, 50 mg QD, 100 mg QD, or placebo. After a review of the clinical data at the December 2021 interim analysis, it was decided that the 2 lowest dose levels (12.5 mg QD and 12.5 mg BID) will be dropped due to a lack of consistent meaningful reduction of blood pressure. Effective with Amendment 4, subjects will be randomized into 4 equal treatment groups (1:1:1:1) to 25 mg BID, 50 mg QD, 100 mg QD, or placebo. All 6 treatment groups will be presented in this analysis plan.

[figure not shown]

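### The PRA comparison in SAP 6.4.1.3 is not placebo-adjusted, so by itself it cannot show the difference in treatment effect that Protocol 9.3.2 asks about

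*SAP*

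**What the plan says.** Protocol 9.3.2 says efficacy analyses will be repeated in the 100 mg groups of the full analysis set, to evaluate "whether there are any differences in the treatment effect depending on the levels of PRA at baseline". SAP 6.4.1.1 frames the primary treatment effect as MLS-101 against placebo, each on top of standard of care.

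SAP 6.4.1.3, headed as the primary efficacy analysis for Part 2, implements the PRA question. Change in office SBP to Weeks 4 and 8 goes into an ANCOVA with "binary PRA (< 1 ng/mL/h versus ≥ 1 ng/mL/h) as a factor" and baseline SBP as covariate, "in the subset of subjects randomized to receive 100 mg QD". The section reports the adjusted mean difference between PRA groups with a 90% CI and p-value. It then lists by-visit descriptive summaries for Part 1 100 mg, Part 2 100 mg, and placebo pooled over the Parts.

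Entry is defined differently from the factor. For Part 1 the "value of PRA must be ≤ 1 ng/mL/h based on morning measurement"; a value above 1 leads to Part 2. Protocol 5.1 takes the entry value from pre-Screening. The protocol synopsis declares all Part 2 analyses exploratory, with no sample-size basis.

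**The concern.** A difference in treatment effect between renin cohorts is a difference of two placebo-adjusted effects. The ANCOVA compares on-drug changes only, so a difference in placebo response between the cohorts would appear as a PRA effect.

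Such a difference is plausible. Subjects are randomized within each Part, but PRA group is not randomized and largely coincides with Part. The Parts differ in:
- the SBP at which subjects are excluded (175 v 160 mmHg) and the potassium limit (5.2 v 4.8 mEq/L), Protocol 5.2;
- fasting for all visits in Part 2 only (Protocol 4.1) and tablet burden (5 v 1 a day, SAP 6.3.5);
- calendar time: the first subject enrolled in July 2021, and Part 2 came with Amendment 5 in February 2022.

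At stake is the conclusion about whether the drug works differently in high-renin patients. That conclusion would carry a p-value and an interval that takes no account of uncertainty in placebo response.

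**Working it through.** **Inputs**
- Level: "confidence intervals and tests of significance will use a 10% (2-sided) significance level" (protocol synopsis), so z = 1.645.
- SD: "assuming a standard deviation of 9 in the subject level changes in SBP from baseline". Applying it to Part 2 is an assumption.
- Sizes: "With 30 subjects planned per arm in Part 1"; about 30 active and 6 placebo in Part 2 (Protocol 4.3).
- For scale: the synopsis works "assuming a 90% 2-sided confidence interval and an effect size of 10.0".
- d, the difference in placebo response between cohorts: not in the documents; assumed, 0 to 5 mmHg.

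**1. The plan's own figure.** SE = 9 × √(1/30 + 1/30) = 2.324; half-width = 1.645 × 2.324 = 3.82. This reproduces the stated ±3.8 for 100 mg v placebo in Part 1. The 100 mg-only PRA contrast, at 30 v 30, has the same width.

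**2. What the ANCOVA estimates.** In each cohort, mean change on 100 mg = placebo response + drug effect. The difference between cohorts is therefore (difference in drug effect) + d. Without placebo subjects the model cannot separate the two terms.

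**3. Equal drug effects, d not zero.** Chance of significance at 10% = Φ(d/2.324 − 1.645) + Φ(−d/2.324 − 1.645).

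| d (mmHg) | d/2.324 | Significant |
|---|---|---|
| 0 | 0 | 10% |
| 2 | 0.86 | 22% |
| 3 | 1.29 | 36% |
| 5 | 2.15 | 69% |

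A simulation of the ANCOVA (2,000 trials per setting) gave 10%, 35% and 68% at d = 0, 3 and 5. The error also runs the other way: with drug effects of 10 and 5 mmHg and a placebo response 5 mmHg larger in Part 2, the average ANCOVA estimate was about 0.

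**4. The placebo-adjusted contrast.** SE = 9 × √(1/30 + 1/30 + 1/30 + 1/6) = 9 × 0.516 = 4.65; half-width = 1.645 × 4.65, about 7.6, twice that of step 1. In the same simulation this interaction test stayed near 10% at d = 0, 3 and 5. Its power at 10% two-sided is 17%, 29% and 69% for true differences of 3, 5 and 10 mmHg. With SD 7, 12 or 15 the half-width is ±5.9, ±10.2 or ±12.7. SAP 2.1 and 2.2 give a 6:1 allocation where the protocol gives 5:1; 36 subjects split 31/5 would give ±8.1.

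**5. The cut and the visit.** Entry is ≤1 / >1; the factor is <1 / ≥1. Taken literally, the mismatch moves only Part 1 subjects with PRA of exactly 1. SAP 6.4.1.3 refers to PRA at baseline, and SAP 6.2.2 defines baseline from the last data before the first double-blind dose. PRA is sampled again at Screening and on Day 1 (Protocol 8.5), so a baseline value could move other subjects across the cut. The documents give no count for either.

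**The case against.** The strongest reply is that the SAP does what the protocol directs. The Protocol 9.3.2 sentence itself names the 100 mg groups, and the amendment log shows a reference to pooled placebo being removed there, so the choice looks deliberate. That stands as an account of how the text arose. It leaves unresolved the tension between a treatment-effect question and an analysis without a comparator.

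A reader might infer that unadjusted changes are compared. They are not: baseline SBP is in the model, so the different SBP limits are partly handled. Above 160 mmHg, where Part 2 entry stops, the adjustment leans on the linear fit. A reader might also count dosing frequency as a difference in drug regimen, but both 100 mg groups take active drug once daily in the morning; only the tablet schedule differs.

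A reader might infer that no placebo comparison exists for Part 2. SAP 5.3 (analyses within each Part) read with 6.4.1.2 (each dose v placebo) can be taken to give one per Part. SAP 6.4.1.3 does not confirm this for Part 2, and nowhere is a contrast between the two effects specified.

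Six placebo subjects are few, and Part 2 is exploratory. Both points are true and limit the weight of the issue. Omitting placebo does not supply the missing information.

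**Conclusion.** The point holds as an analysis-choice issue in an exploratory part of the trial. The 100 mg-only ANCOVA estimates a baseline-SBP-adjusted difference between non-randomized cohorts; it does not by itself estimate a difference in treatment effect. Its interval of about ±3.8 mmHg compares with about ±7.6 for the placebo-adjusted contrast, both assuming SD 9 and the planned sizes. The 22% to 69% significance rates are conditional on assumed placebo differences of 2 to 5 mmHg. At zero difference the rate is the nominal 10%, and nothing in the documents says which applies.

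Two stronger readings are not supported. A reader might infer that PRA is wholly confounded with Part; if the Day 1 value defines the factor, subjects can cross the cut and the two are not identical. A reader might also infer that the cut mismatch distorts the result; as written it touches only values of exactly 1, so it is secondary.

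**What to change.** - Add to SAP 6.4.1.3 an exploratory model on the 100 mg QD and placebo subjects of both Parts, with treatment, cohort (Part 1, Part 2), treatment-by-cohort and baseline SBP. Report the interaction with its 90% CI as the placebo-adjusted between-cohort comparison. SAP section 7 already allows pooling for some exploratory analyses.
- State beside it that this is still a non-randomized cohort contrast with low power. It removes additive differences in placebo response, but not other effect modifiers that differ by Part, so it does not isolate PRA.
- Label the 100 mg-only ANCOVA as a descriptive between-cohort difference.
- Change the PRA cut to ≤1 v >1, and state whether the pre-Screening or the Day 1 value defines the factor.
- Reconcile the Part 2 allocation ratio between SAP and protocol.

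The cost is SAP wording and one extra model on data already collected. The price is an openly wider interval, about twice the width of the present one.

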6.4.1.4 Sensitivity analysis

To test the robustness of the primary efficacy analysis, the following sensitivity analyses will be performed in the FAS:

An analysis where missing endpoint data resulting from ICES of type 4 and 5 will be handled assuming that the clinical course for either treatment group follows that of the placebo group. The jump-to-reference method (Carpenter et al., 2013) is used, with placebo as the reference group.

Missing data as a result of an ICE are imputed as the mean of the placebo group for that visit, regardless of the treatment group the subject was in.

6.4.1.5 Supplementary analyses

An additional Estimand will be considered for analyzing the primary efficacy endpoint, regardless of intercurrent events post-baseline, defined by the following attributes:

| Attribute | Description |
|--------------------------|--|
| Treatment | 5 MLS-101 dose levels (12.5 mg BID, 25 mg BID, 12.5 mg QD, 50 mg QD, or 100mg QD) vs placebo |
| Population | Subjects with uncontrolled hypertension (hypertensive despite receiving ≥ 2 antihypertensives) as defined by the inclusion/exclusion criteria in the protocol |
| Endpoint | Change in office-measured SBP from baseline at Study Week 8 |
| Intercurrent events | The occurrence of intercurrent events is considered irrelevant in defining treatment effect; the values of the endpoint will be used regardless of whether subject experiences an intercurrent event. This corresponds to a treatment policy strategy . |
| Population-level summary | Mean change in SBP from baseline at Study Week 8 |

Under the alternative Estimand, the same analyses above will be repeated as for the primary efficacy analysis

The primary efficacy analysis will also be repeated on the per-protocol analysis set.

6.4.1.6 Subgroup Analyses for Primary Efficacy

The change in office-measured SBP from baseline at Study Week 8 in Part 1, along with corresponding 90% confidence intervals will be calculated by treatment group for each of the subgroups of the FAS defined in Section 6.2.5 for both the primary Estimand described in Section 6.4.1.1 and the supplemental Estimand described in Section 6.4.1.5. These results will be considered exploratory.

Subgroup analyses will not be performed for Part 2, due to the small sample sizes, though the primary efficacy endpoint in Part 2 will be summarized by subgroup.

6.4.2 Secondary Efficacy Outcome Analyses

All secondary efficacy endpoints analyses will be considered supportive and any inferential statistics will be considered descriptive in nature. No adjustment for multiplicity will be performed. Unless otherwise stated, all secondary efficacy endpoints analyses will be based on the FAS.

6.4.2.1 24-hour ABPM

The ABPM will be measured in the clinic at baseline and end of treatment (EOT). If, for any reason, the ABPM procedure is deemed a failure, it can be repeated, and therefore no imputation will be employed regardless of use of rescue medications. The last available post-baseline ABPM assessment will be considered as EOT.

Additionally, ABPM is also collected at the end of Study Week 4 in Part 2. If a repeat test is performed, it supersedes the original test results for Week 4. Tests denoted as Week 4 cannot be flagged as EOT, even if no later post-baseline assessment exists.

The ABPM measurements will be included regardless of the QC Status of individual readings or the derived variables. QC statuses of 'Failed' will be noted in the listings.

Specific derived variables based on ABPM measurements include mean 24-hour, mean Daytime, and mean Nighttime of SBP, DBP, and heart rate. Mean 24-hour Mean Arterial Pressure is derived as

$$(\text{mean 24-hour SBP} + \text{mean 24-hour DBP})/2$$

Each of these derived variables will be summarized by treatment group and visit using descriptive statistics.

Change from baseline to EOT in 24-hour mean SBP (and DBP) based on ABPM will be analyzed using an ANCOVA with a term for treatment group and a baseline mean 24-hour value as a covariate.

The nighttime dip is defined as

$$100\% \times (\text{mean daytime SBP} - \text{mean nighttime SBP}) / \text{mean daytime SBP}$$

It is expressed as a percentage and will be summarized by treatment group and visit using descriptive statistics. In addition, the number and percentage of subjects with nighttime dip in each of the dipper categories (Bloomfield & Park, 2015) will be presented by treatment group and visit.

The categories are:

- < 10%
- 10-20% inclusive
- > 20%

All ABPM variables will be listed.

6.4.2.2 Change from Baseline in SBP by Week

Change from Baseline in SBP at each visit will be analyzed as per the primary efficacy analysis described in Section 6.4.1.2.

In addition, this analysis will be repeated by subgroup, for each of the subgroups listed in Section 6.2.5.

6.4.2.3 Change from Baseline in DBP by Week

Change from Baseline in DBP at each visit will be analyzed as per the primary efficacy analysis described in Section 6.4.1.2, with the exception that baseline DBP will replace baseline SBP as a fixed covariate in the model.

In addition, this analysis will be repeated by subgroup, for each of the subgroups listed in Section 6.2.5.

6.4.2.4 Proportion with BP <130/80 mmHg

Each subject will be assessed as a success if the Week 8 value for SBP is ≤ 130 mm Hg and DBP ≤ 80 mm Hg; a subject will be assessed as a failure otherwise. The number and proportion of subjects will be provided by treatment group.

Number and proportion of subjects who achieve only the SBP or DBP goal (but not both) will be provided as well. Subjects missing an assessment at Week 8 or who have received rescue medications will also be considered as failures.

Relationship between success (as defined above) and SBP levels at baseline (mm Hg) will be evaluated graphically using by-treatment scattered boxplots of baseline SBP with success/failure marked for each subject.

